that more directly measure neural activity, such as scalp EEG, should be incorporated into studies of chemobrain. Currently, only a handful of electrophysiological studies have examined the impact of chemotherapy treatment on a single electrophysiological component (i.e. P300), which was evoked by a non-demanding cognitive task. Further electrophysiological studies must incorporate more demanding tasks that challenge specific attention mechanisms. Given the limitations of current research on the neural mechanisms of chemobrain, it is still unclear how chemotherapy affects the functional integrity of the frontoparietal attention network. Together, cognitive and electrophysiological measures of attention provide a powerful tool for isolating neural mechanisms influenced by chemotherapy treatment. Thus, more work should be devoted to more rigorous and targeted electrophysiological studies of attention, which will be integral to separating neural from non-neural factors associated with chemobrain.

Third, neuropsychological tests typically recruit multiple cognitive domains, limiting specificity of impaired cognitive functions. For example, most paper-and-pencil tests recruit additional speed of processing and motor control abilities during task performance. Furthermore, methods for measuring task-related neural activity during neuropsychological testing are yet to be established. In contrast, computer-based cognitive tests allow researchers to selectively measure specific cognitive processes by manipulating display timing and stimulus characteristics, thus providing insight into how different cognitive systems interact during task performance. Furthermore, numerous studies have linked performance in computer-based cognitive tasks with neural function through MRI and EEG methods. In particular, the high temporal resolution of EEG methods demands cognitive testing instruments that provide concurrent temporal resolution through precisely timed stimulus presentation. Thus, studies of chemotherapy-related cognitive impairment would benefit from the incorporation of more sophisticated cognitive batteries.

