- Health and Mobility Questionnaires. Several questionnaires will be used to determine health, mobility, psychosocial status, and medication usage; these measures will be used to control for non-neural factors that may contribute to cognitive health. Questionnaires to be administered include: Beck Depression Inventory (depression screen), medication usage form (list of current medications), health survey questionnaire (inventory of health status and activity level), and life space questionnaire (mobility inventory).

Attention Battery

The goal of Specific Aim 1 is to construct a cognitive battery that decomposes the general construct of attention into its underlying mechanisms, enabling the examination of chemotherapy-related impairments across multiple processes of attention. To this end, we selected tasks that isolate four mechanisms of attention: 1) *processing speed* – time required to attend and recognize an item, 2) *inhibitory control* – ability to ignore irrelevant items, 3) *disengagement speed* – time required to release attention from an item, and 4) *storage capacity* – number of items that can be simultaneously attended.

Attention mechanisms measured by our battery are relevant to daily activities in the real world, such as holding a conversation in a noisy diner. For example, while listening to a friend speaking (i.e. target stimulus), the sounds of other patrons speaking (i.e. irrelevant stimulus) or dishes crashing to the floor (i.e.

distractor stimulus) compete for our limited attentional resources, thus providing opportunities for our attention to be distracted away from our friend speaking and towards an irrelevant stimulus. This hypothetical scenario provides examples of the four attention mechanisms measured in Specific Aim 1: speed at which speech of friend can be processed to understanding (*processing speed*), ability to ignore other patrons speaking and dishes crashing (*inhibitory control*), speed at which attention can be released from a distracting stimulus and re-engaged with the conversation (*disengagement speed*), and how much information from the conversation can be held in memory (*storage capacity*).

Collectively, our cognitive battery will offer millisecond-by-millisecond resolution of attention processes engaged by participants during task performance.

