Capture task. Capture tasks⁷⁰⁻⁷⁴ are an ideal candidate for studying attention because they offer experimenters a tool to precisely measure the *cost of processing an irrelevant stimulus* within a capturing display (*inhibitory control* mechanism) and the *timecourse of releasing attention* when it is captured by an irrelevant stimulus (*disengagement speed* mechanism).

In this task (Figure 2), participants are instructed to identify a target item (e.g. a green square with a notch on one side) presented among multiple distractor items within a search display; prior to the search display, a brief capture display is presented that contains a colored distractor item similar (contingent condition) or dissimilar (singleton condition) to the target color. Performance is measured as response time to correctly identify and respond with the location of the notch in target items. Previous studies have demonstrated: 1) longer reaction times in the contingent condition relative to the singleton condition, because attention is more likely to be distracted by a contingent stimulus that matches the target stimulus color, and 2) shorter reaction times in both conditions at longer inter-stimulus intervals (ISI; time difference between capture display and search display), because attention is more likely to disengage from the capturing stimulus prior to the onset of the search display when ISIs are longer.

In the current proposal, we will be able to directly measure the effects of chemotherapy treatment on inhibitory control mechanisms as they apply to the suppression of an irrelevant stimulus and disengagement mechanisms as they apply to the release of captured attention from an irrelevant stimulus.

Figure 2: Capture Task Schematic

Filtering task. Filtering tasks^{75,76} are an ideal candidate for studying attention because they offer experimenters a tool to precisely measure the *amount of information* that can be simultaneously attended (*storage capacity* mechanism) and the efficiency to *filter out irrelevant information* embedded among relevant information (*inhibitory control* mechanism).

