 - Capture condition, stimulus ISI, and treatment group on Pd (amplitude, latency) and N2pc (amplitude, latency) measures during the Capture Task of the Attention Battery
 - Filtering condition, storage load, and treatment group on N2pc (amplitude, latency) and CDA (amplitude) measures during the Filtering Task of the Attention Battery
 - Treatment group on N2pc (amplitude, latency) and Pd (amplitude, latency) measures during the Visual Search Task of the Driving Simulation

Our primary hypothesis is that chemotherapy treatment negatively affects core neural mechanisms of attention. Here, we present predictions for how chemotherapy would affect outcome measures from each task and electrophysiological measure, where specific predictions are given based on how impairments in different attention mechanisms would affect the pattern of data observed in each task.

Attention Measures

Capture task. Two dissociable mechanisms of attention are measured in this task. First, *inhibitory control* is required to suppress the processing of the capture display; inhibitory control mechanisms will be tracked by the Pd component. Second, *disengagement speed* is required to rapidly release attention from capture displays to prepare for the subsequent search display; disengagement mechanisms will be tracked by the N2pc component. There are three possible predictions for impairments in each attention measured in the capture task.

- Hypothesis 1: Inhibition effect/No disengagement effect. Relative to comparison subjects, this hypothesis predicts a chemotherapy-related: 1) increase in response time differences between contingent and singleton capture conditions, 2) increase in Pd amplitude, and 3) decrease in N2pc amplitude.
- Hypothesis 2: No inhibition effect, disengagement effect. Relative to comparison subjects, this hypothesis predicts a chemotherapy-related: 1) increase in response times in both capture conditions, 2) decrease in N2pc amplitude, and 3) no difference in Pd amplitude.

Hypothesis 3: Inhibition effect, disengagement effect. Relative to comparison subjects, this hypothesis predicts a chemotherapy-related: 1) increase in response times in both capture conditions, 2) increase in response time differences between contingent and singleton capture conditions, 3) increase in Pd amplitude, and 4) decrease in N2pc amplitude.

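### The capture-task predictions read disengagement from slower responding overall, not from the inter-stimulus-interval (ISI) effect, so general slowing can be taken for a disengagement deficit

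*Combined protocol and SAP*

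**What the plan says.** Section 5.0 (Attention Battery) treats processing speed and disengagement speed as separate mechanisms and defines the first as "time required to attend and recognize an item". The Capture task description says that earlier work found "shorter reaction times in both conditions at longer inter-stimulus intervals", and explains this by attention having had time to let go of the capturing item before the search display appears. Table 2 marks the Capture Task for processing speed, inhibitory control and disengagement speed. It is the only Specific Aim 1 task marked for processing speed.

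Section 10.0 (Statistical Analysis) puts capture condition, ISI and treatment group in the RT model, and uses the same factors for Pd and N2pc. Under Attention Measures, Capture task, it counts two mechanisms for the task, inhibitory control and disengagement, and states that "disengagement mechanisms will be tracked by the N2pc component". Its three predicted patterns, all relative to comparison subjects, are:

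- Hypothesis 1 (inhibition, no disengagement): "increase in response time differences between contingent and singleton capture conditions, 2) increase in Pd amplitude, and 3) decrease in N2pc amplitude".
- Hypothesis 2 (disengagement, no inhibition): "increase in response times in both capture conditions, 2) decrease in N2pc amplitude, and 3) no difference in Pd amplitude".
- Hypothesis 3 (both): "increase in response times in both capture conditions, 2) increase in response time differences between contingent and singleton capture conditions", with higher Pd and lower N2pc amplitude.

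**The concern.** Specific Aim 1 sets out to split attention into its component mechanisms. Section 2.0 (Motivation) criticises existing tests because "most paper-and-pencil tests recruit additional speed of processing and motor control abilities during task performance". A prediction that rests on overall RT brings the same mixture back: slower recognition or slower responding raises RT in both conditions even when attention is released at the normal rate.

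The protocol gives reasons to expect some general slowing. Section 2.0 lists processing speed among the most frequent deficits, alongside attention and memory, and Section 5.0 expects anemia with possible fatigue in these patients. The study is a pilot meant to supply effect sizes for later studies, so an effect size filed under the wrong mechanism would be carried forward.

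**Working it through.** **1. The three patterns side by side (Section 10.0, Capture task).**

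| | RT in both conditions | Contingent minus singleton RT | Pd amplitude | N2pc amplitude | ISI |
|---|---|---|---|---|---|
| Hypothesis 1: no disengagement effect | not stated | larger | higher | lower | not mentioned |
| Hypothesis 2: disengagement only | higher | not stated | no difference | lower | not mentioned |
| Hypothesis 3: both | higher | larger | higher | lower | not mentioned |

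The N2pc column is constant, so it cannot separate disengagement from its absence. Hypotheses 1 and 3 differ only in the overall RT rise. Pd separates Hypothesis 2 from the other two, but the plan assigns Pd to inhibition. Section 5.0 also links N2pc amplitude to target enhancement, and Table 2 does not mark N2pc for disengagement. The disengagement label therefore rests on overall RT.

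**2. The plan's own figure.** Section 10.0 equates 0.65 SD with a 10% RT difference, using a healthy-control mean of 1394.75 and SD of 213.23. Check: 0.10 × 1394.75 = 139.5, and 139.5 / 213.23 = 0.654. This reproduces. The plan gives neither the unit nor the task for these values.

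**3. What general slowing does to each contrast.** Let D be a constant delay added to every RT.

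- Overall RT: the group difference is D in both conditions, so the RT part of Hypothesis 2 is met.
- Group-by-ISI: (short + D) − (long + D) = short − long, so the expected group difference is zero whatever the task effects are.

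**4. Simulation.** Two groups are compared at one visit, with 2 conditions × 2 ISIs and 20,000 runs. From the plan: mean 1394.75, between-subject SD 213.23, 15 per group (pilot) or 32 per group (future study). Assumed, because the documents give no values: condition difference 50, residual SD per cell 40, ISI effect 50 to 200, in the units of the stated mean. The RT prediction counts as met when RT is significantly higher in each condition.

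| Scenario | n per group | Two-sided alpha | RT higher in both conditions | Group-by-ISI significant |
|---|---|---|---|---|
| Constant delay of 139.5, disengagement intact | 15 | 0.05 | about 37% | about 5% |
| Same | 15 | 0.01 | about 16% | about 1% |
| Same | 32 | 0.05 | about 70% | about 5% |
| Same | 32 | 0.01 | about 45% | about 1% |
| All RTs × 1.10, disengagement intact | 15 | 0.05 | about 34% | 6 to 26% |
| Same | 32 | 0.05 | about 65% | 8 to 50% |
| Disengagement deficit only: short-ISI RT raised by half the ISI effect | 15 | 0.05 | 3 to 8% | 38% to nearly 100% |

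The simulation lets the true ISI effect vary only by group, not from person to person, so the last column is optimistic for a real deficit.

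**5. Choice of scale.** Proportional slowing enlarges raw contrasts, as the × 1.10 rows show. A constant delay shrinks log contrasts. For an assumed condition cost of 80, the log cost is ln(1474.75 / 1394.75) = 0.056 without the delay and ln(1614.2 / 1534.2) = 0.051 with it, about 9% smaller. Neither scale is immune to both forms of slowing.

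**6. Which ISI contrast.** Section 5.0 describes the ISI effect in both conditions. A release delay common to both leaves the condition-by-ISI contrast unchanged, so that contrast would miss it. It is also noisier: with independent cell errors of SD 40, the ISI contrast averaged over conditions has SD √(1600/2 + 1600/2) = 40, and the condition-by-ISI contrast has SD √(4 × 1600) = 80.

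**The case against.** The strongest defence is that each hypothesis is a joint pattern. Hypothesis 2 needs lower N2pc and unchanged Pd as well as slower RT, so purely motor slowing with unchanged N2pc fits none of the three. This stands, and the simulated rates concern the RT part alone. It does not close the gap, because slowing that comes with lower N2pc still fits, and lower N2pc is predicted whichever mechanism is affected.

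ISI is also in the planned model, which covers within-subject, between-subject and mixed effects with confidence intervals, so a group-by-ISI estimate could be produced. That is true and makes the repair cheap. What is missing is any statement that this estimate is the one that bears on disengagement.

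Planned covariates such as anemia and depression might absorb some slowing. They enter only if linked to performance, and none is a measure of general response speed.

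A reader might infer that general slowing would necessarily be reported as a disengagement deficit, that individual patients would be so classified, or that proportional slowing would also be declared an inhibition effect. The documents support none of these. The predictions are for groups, they are joint with the EEG measures, and both inhibition patterns also require higher Pd.

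**Conclusion.** The point holds as a defect of specificity in the stated predictions. Section 5.0 identifies disengagement by the change in RT across ISI, whereas Section 10.0 identifies it by higher RT in both conditions together with an N2pc change common to every hypothesis. General slowing with lower N2pc can be read as a disengagement deficit, and a true deficit confined to short ISIs can go unrecognised.

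The reasoning from the table of patterns, and the zero group-by-ISI expectation under a constant delay, need no assumed values. The percentages do. They rest on assumed task effects, on an RT mean and SD that the plan does not assign to this task, and on a comparison at one visit rather than change from baseline. The 10% is a detectable difference quoted for a future study, not a forecast of slowing. Correcting this before analysis is advisable; it does not undermine the data collection.

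**What to change.** In Section 10.0, Capture task:

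- In Hypotheses 2 and 3, name the group-by-ISI (by visit) contrast on RT, averaged over capture conditions and tested two-sided, as the behavioural test of disengagement. Give group-by-condition-by-ISI as secondary.
- State that the overall group difference in RT is interpreted as general or processing-speed slowing, the mechanism that Table 2 lists for this task and that currently has no capture-task prediction.
- Report log RT beside raw RT as a sensitivity analysis, and say which direction each scale is biased under proportional and constant slowing.

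The cost is wording only, since ISI is already recorded and modelled. The downside is that the interaction may be estimated less precisely than the overall mean in a pilot of 15 per group, so it should be reported with its confidence interval.

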Cognitive assessment. Clinical neuropsychological exams to be used in the current proposal include: *Mini-Mental State Examination*^{5,14,20} (MMSE; mental status, dementia screening tool), *Trails A and* B^{1-4,6-11,15,18,20,22-24,35} (processing speed), *Useful Field of View* (UFOV; processing speed, divided attention, inhibitory control), *Paced Auditory Serial Attention Task*^{18,23} (PASAT; working memory, arithmetic), *Stroop*^{2,3,5-9,12,17,23,24} (executive function).

Vision assessment. Clinical measures of visual deficits to be used include: visual acuity, contrast sensitivity (discrimination threshold for light and dark boundaries), frequency doubler task (visual field deficits), visual function questionnaire (self-reported impairment of visual function), and neuro-ophthalmology supplement (NAS)-10 (self-reported impairment of visual function).

Retinal anatomy. Retinal anatomy is an underutilized tool for studying the link between brain disease and cognitive impairment, particularly in cancer populations. Optical coherence tomography (OCT) provides an easy, non-invasive and reliable method of studying retinal anatomy in healthy and diseased populations. With an axial resolution of 4-6 micrometer, the new generation spectral domain OCT can reliably identify the various neuronal layers of the retina.

Previous work has demonstrated a link between retinal anatomy integrity and neurodegeneration¹¹⁰, particularly in Alzheimer's Disease¹¹¹, Parkinson's Disease¹¹², and Multiple Sclerosis¹¹³. In the current proposal, OCT measurements will allow us to determine the presence of neurodegeneration of the retina in cancer patients receiving chemotherapy, and link declines in retinal anatomy integrity with concurrent declines in cognitive performance. Thus, this method has potential to further develop non-invasive and rapid imaging biomarkers for chemotherapy-related cognitive impairment.

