While we realize we will not have sufficient power to declare smaller effects statistically significant, as this is a pilot study, it will allow us to estimate effect sizes for a number of outcomes to conduct fully powered studies. In future large-scale confirmatory studies, with a sample size of 32 per group, we will have 80% power to detect a standardized effect size of 0.65 (a medium to large effect) for within group changes, and an effect size of .9 for between group differences. These power calculations assume a two-tailed alpha of 0.01 to informally adjust for multiple comparisons and multiple testing. A standardized effect size of 0.65 corresponds to a 10% difference in response time from healthy controls (mean=1394.75, standard deviation = 213.23). This sample size will allow adequate power to detect medium to large effects within group, and large effects between groups.

Statistical Analysis. To assess the data collected, for each group, we will first produce frequency tables, calculate descriptive statistics, and create univariate graphs (e.g. box-plots, histograms) on the

predictor and response variables to investigate distributional properties and check for outliers in the data. Although the specific statistical models that we will use to test our formal hypotheses and to calculate confidence intervals will depend on the outcome distributions that we observe in our data, we anticipate using linear mixed models and generalized linear mixed models, as appropriate. This modeling approach allows us to properly account for the distribution of the outcome measure while also properly modeling repeated effects and adjusting for potentially confounding variables. Confidence intervals of all effects will be calculated in order to assess clinical significance of statistical results.

We will employ linear mixed models and general linear models to **assess** within-subject, betweensubject, and mixed effects of:

- Behavior:
 - Capture condition, stimulus ISI, and treatment group on response time measures in the Capture Task
 - Filtering condition, storage load, and treatment group on response accuracy measures in the Filtering Task
- Driving simulation:
 - Treatment group on response time measures in the Visual Search Task
 - Treatment group on lead car distance variability, brake time, and number of incursions during the Car Following Task
- □ Electrophysiology:

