Visual search task. According to the hypothesis that chemotherapy treatment impairs *deployment* speed, a chemotherapy-related increase in response time should be observed because attentional resources will be slower to deploy; furthermore, changes in the complexity of the driving environment (e.g. road hazards, high visual load) would lead to longer response times as a function of complexity because attentional resources would be more engaged with more complex environments, leading to poorer *inhibitory control*. For electrophysiology, this hypothesis predicts chemotherapy-related reductions in N2pc amplitude and increases in N2pc latency – because lower inhibitory control would lead to a lower probability of being prepared to deploy attention towards the task-relevant search display.

Auxiliary Measures

Cognitive assessment. According to the hypothesis that chemotherapy impairs attention mechanisms, we predict impairments in performance across neuropsychological exams within the cognitive assessment, because these tests measure cognitive abilities directly related to attention. For example, memory tests (e.g. CVLT, BVRT) require attention to successfully encode information into memory storage; failures of attention would lead to failures of encoding into memory, and thus impairments in memory retrieval.

Vision assessment and retinal anatomy. Our hypothesis is that chemotherapy negatively affects higher-level attention mechanisms, such that attention impairments cannot be explained by impairments in low-level visual processes. Therefore, we predict no changes across vision assessment exams and questionnaires. Conversely, given the hypothesis that chemotherapy leads to morphological changes in

neural structures, and the fact that the retina is a neural structure, we do predict reductions in retinal and optic nerve thickness.

C-Reactive Proteins. According to previous work, circulatory levels of C-Reactive Proteins (CRPs) increase in response to inflammation, including tumor genesis and growth. We therefore predict an increase in CRP levels in HM patients relative to healthy controls; furthermore, we predict further increase in CRP levels in HM patients receiving chemotherapy relative to HM patients receive best supportive care treatment. Finally, we hypothesis that increases in CRP levels will predict concurrent increases in attention impairment both within and between research participants.

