Section 11.0 Records to be Kept:

The following forms will be collected during each study visit, and stored in locked filing cabinets within keycard restricted lab space in the Mind and Brain Health Labs (first floor of Clarkson Doctor Building North). Data collection forms will be entered electronically into a study database on a password-protected, encrypted, dedicated research network.

- Phone Screen Script
- Patient Tracker
- Demographic Form
- □ MMSE Data Collection Form
- □ HM Data Collection Form
- □ Hematopoietic Cell Transplant Co-Morbidity Index (HCT-CI)
- Beck Depression Index
- □ Life Space Questionnaire
- □ Medication Form
- □ Health Survey
- □ Visual Function Questionnaire
- □ Far Visual Acuity Form
- □ Contrast Sensitivity Form
- □ Frequency Doubler Task (FDT) Record Sheet
- □ Trails A Data Collection Form
- □ Trails B Data Collection Form
- □ Stroop Test Participant Form
- □ Stroop Test Scoring Form
- □ PASAT Scoring Sheet
- □ UFOV Scoring Sheet

In addition to the forms indicated above, electronic records of performance during the cognitive, electrophysiological, and simulation batteries will be maintained in their raw form on password protected computers. After completing each testing battery, raw data will be stored on a password-protected, encrypted, dedicated research network.

Section 12.0 Patient Consent: The consent form must adhere to the guidelines established by the Institutional Review Board of the University of Nebraska Medical Center.

Section 13.0 References

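### The hypothesis that low-level vision does not explain attention loss is checked only indirectly and with low power, because no listed model or named control measure includes the vision scores collected

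*Combined protocol and SAP*

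**What the plan says.** Section 10.0, Auxiliary Measures, offers as a hypothesis that chemotherapy acts on attention at a higher level, so that "attention impairments cannot be explained by impairments in low-level visual processes. Therefore, we predict no changes across vision assessment exams and questionnaires". The first part of that quote belongs to the hypothesis, and the second is a prediction derived from it. The plan gives no margin for no change and no model for the vision scores. The same paragraph then says of the eye itself that "we do predict reductions in retinal and optic nerve thickness".

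The Statistical Analysis part of Section 10.0 lists the model terms for each outcome. The first entry is "Capture condition, stimulus ISI, and treatment group on response time measures in the Capture Task". The filtering entry has filtering condition, storage load and group. The driving entries have group alone. The EEG entries repeat the task factors, or use group alone for visual search. None has a vision term.

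Section 5.0, Experimental Control Measures, names comorbidity, anemia and a set of questionnaires (depression, medication, health, life space). It says of the questionnaires that "these measures will be used to control for non-neural factors that may contribute to cognitive health". No vision test or visual function questionnaire is among them.

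The vision data are nevertheless planned. Section 5.0, Vision assessment, lists acuity, contrast sensitivity, the frequency doubler task and two visual questionnaires. Section 11.0 lists the matching forms, for example the "Contrast Sensitivity Form", among those collected at each study visit.

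**The concern.** Whether vision explains an attention effect is a question about the attention models: does the group contrast hold up once each person's vision is taken into account? A comparison of mean vision scores does not settle that. Vision could change without explaining the effect, or a shift too small to detect in this sample could explain part of it.

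The capture, filtering and visual-search displays are all visual. Several of the patterns that Section 10.0 would read as attention deficits are also what a general visual loss would produce: slower responses in both capture conditions (read as a disengagement effect), lower accuracy in both storage and filtering conditions (read as a capacity effect), and slower visual search while driving. Because the plan itself predicts retinal and optic nerve thinning, it cannot set a visual-input route aside in advance. At stake is whether the pilot's effect sizes, which are meant to inform fully powered studies, can be read as effects on attention.

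**Working it through.** **1. Method check against the plan's own figure.** Section 10.0 states 80% power with 32 per group at two-tailed alpha 0.01, for 0.65 SD within group and 0.9 SD between groups. Exact noncentral t:
- Within: df 31, noncentrality 0.65 × √32 = 3.677, critical value 2.744, power 0.817.
- Between: df 62, noncentrality 0.9 × √(32/2) = 3.600, critical value 2.657, power 0.823.

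Both agree with the stated 80%, so the same method is used below. That power statement concerns a future study. The plan gives no figure for vision.

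**2. How informative are unchanged vision scores at 15 per group?** The 15 comes from Section 10.0. The 0.5 SD shift and alpha 0.05 are assumptions, because no alpha is stated for the pilot.
- Between groups: df 28, noncentrality 0.5 × √(15/2) = 1.369, critical value 2.048, power 0.262. A real shift is missed 1 − 0.262 = 74% of the time (90% at alpha 0.01).
- Within group: noncentrality 0.5 × √15 = 1.936, power 0.438, missed 56% of the time.
- The 95% interval for a between-group vision difference has half-width about 2.048 × √(2/15) = 0.75 SD. A null result would still be compatible with a sizeable shift.

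**3. What could omitted vision do to an attention contrast?** Assume no direct attention effect, a vision shift δ (in SD) between chemotherapy and comparison groups, and a within-group vision-attention correlation r. The documents give neither δ nor r. The spurious attention shift is δ × r. Rejection at alpha 0.05 is the two-sample t power at that shift with 15 per group.

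| δ | r | Spurious shift (SD) | Rejection, alpha 0.05 |
|---|---|---|---|
| 0.3 | 0.3 | 0.09 | about 6% |
| 0.5 | 0.5 | 0.25 | about 10% |
| 0.7 | 0.7 | 0.49 | about 26% |

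In the mid-case, rejection at alpha 0.01 is about 2.5%. On the response-time SD of 213.23 in Section 10.0, 0.25 SD is 0.25 × 213.23 = 53 units.

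**4. What does adjustment recover?** In simulation with vision measured without error, the adjusted contrast averages about 0 and rejection is about 5%. With a vision score of reliability λ, the remaining shift is δ × r × (1 − λ). In the mid-case this is 0.25 × 0.3 = 0.075 SD at λ = 0.7 and 0.25 × 0.5 = 0.125 SD at λ = 0.5. Both reliabilities are assumed. Adjustment removes most of the shift when vision is well measured, and less when it is not.

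**5. Which outcomes are exposed?** A loss that affects both conditions of a task tends to cancel in contingent-minus-singleton response time and in filtering-minus-storage accuracy. Overall capture response time, accuracy in both filtering-task conditions, and driving visual-search response time have no such protection.

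**The case against.** A reader might infer that the plan concludes from unchanged vision scores that vision plays no part. The text does not support that. The statement is a hypothesis, and unchanged vision is predicted from it. Nor is the hypothesis wholly untested: a clear fall in vision scores would contradict the prediction. The fair criticism is that this check is indirect, weak at this sample size, and without a margin.

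It can also be said that the models are not closed. Section 10.0 leaves their final form to the data and promises adjustment for potential confounders. It names none, so vision is neither included nor excluded. The cofactor rule in Section 5.0 concerns factors unrelated to chemotherapy, so a visual loss caused by treatment would not clearly fall under it. Retinal imaging does have a stated control role in Section 5.0, but it measures structure rather than visual function, and only 10 healthy controls are to be scanned. Section 3.0 requires normal or corrected vision of patients, which deals with entry and not with later change.

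Another tempting reading is that visual loss and attention loss cannot be told apart in any outcome. That goes too far, because the within-task contrasts are partly protected.

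Two further points stand. The size of the distortion rests on assumed inputs, and its upper end needs both at 0.7. If chemotherapy causes the visual loss, vision is a mediator and the unadjusted contrast is a legitimate total effect.

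**Conclusion.** The concern holds as a gap in specification. The plan hypothesizes that low-level vision does not explain attention loss and lists the data needed to examine this, but it names no analysis that relates the two. The check it does imply would miss a 0.5 SD between-group vision shift about three times in four (alpha 0.05, 15 per group). The illustrated distortion of 0.09 to 0.49 SD, 0.25 SD in the mid-case, depends on an assumed vision shift and correlation. It shows what is possible, not what is expected. It applies mainly to the outcomes that are not within-task differences. In a pilot meant to estimate effect sizes, this is a worthwhile and inexpensive improvement. It does not invalidate the main models.

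**What to change.** In Section 10.0, keep the main models as they are. For the capture, filtering, visual-search and EEG outcomes, add one prespecified secondary model that includes same-visit acuity, contrast sensitivity and frequency-doubling scores. Report the chemotherapy contrast with and without these scores, with a confidence interval for the change. Base any statement that low-level vision does not explain the effect on that comparison, not on a non-significant change in vision scores. Describe the adjusted model as a direct-effect sensitivity analysis, since vision may be a mediator, and note that measurement error in the vision tests leaves some of the shift in place.

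Confirm in the Section 7.0 schedule that the vision tests are done at every visit. The schedule has no vision row, and its listed items already fill the visit (40 + 15 + 20 + 45 + 10 + 10 + 10 = 150 minutes, the stated 2.5 hours). The abstract groups vision with the neuropsychological tests, so they may sit in that row. The Section 11.0 list does not settle it, because it also includes the demographic form, which Section 7.0 schedules at induction only.

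The cost is a paragraph, one extra model per outcome, and wider intervals in that model. For a two-group contrast, three covariates take residual df from 28 to 25. If three uncorrelated scores each differ by an observed 0.5 SD between groups, the variance factor is about 1 + 3 × 0.25 × 7.5/28 = 1.20, so the standard error rises by about 10% before any gain from variance that vision explains.
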